5.2.2 Key Secondary Endpoints

Data supporting the following endpoints will be collected for both the Randomized Studies as well as the VLU Study. The following endpoints will be compared for the Randomized Studies and will be evaluated for the VenaSeal™ system for the VLU Study.

1. Anatomic closure of the primary target superficial truncal vein at 6 months, defined as DUS showing vein closure along the entire treated vein segment with no discrete segments of patency exceeding 5 cm after VenaSeal™ system and ETA procedures, or the absence of refluxing or residual primary target vein after surgical stripping procedures.
2. Time to return to work as reported by the patient.

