7.8	Interim Analyses.....	23
7.9	Evaluation of Objectives	23
7.10	Safety Evaluation.....	52
7.11	Health Outcomes Analyses	53
7.12	Changes to Planned Analysis.....	53
8.	Validation Requirements.....	54

9. References	54
10. Statistical Appendices.....	54

1. Version History

Version	Summary of Changes	Author(s)/Title
1.0	
 Not Applicable, New Document 	[name], Principal Statistician
2.0	
 Update to note that elimination of truncal reflux will be summarized without hypothesis testing for the VenaSeal vs. Surgical Stripping Study, due to halted enrollment in sections 4.1, 7.5 and 7.9. Updated study design consistent with CIP changes in sections 5.1, 5.2, 6.2 and 7.9.3 (halting of Venaseal vs. Surgical Stripping study enrollment and reducing follow-up to 12 months and reduction in sample size of the VLU study) Add note on handling of VenaSeal vs. Surgical Stripping study data collected beyond 12 months in section 7.1.1 Added the scoring algorithm for the VenousTSQe and VenousTSQs in section 7.9.1.1.4 Added test for superiority in non-inferiority is met in section 7.9.1.2.3 Document updated using new template. 	[name], Principal Statistician
3.0	
 Re-organized the document so that each study endpoint is enumerated and the corresponding hypothesis, endpoint definition, analysis methods and analysis population are provided Return-to-work endpoints, return-to-normal activities, anatomic closure endpoints all revised use a time-to-first-event analysis to allow for censoring and incorporation of unscheduled follow-up visits Reintervention and healthcare utilization endpoints are revised to use a rate-based calculation to allow for potential recurrent events and differences in follow-up time Updated scoring of the VenousTSQe and VenousTSQs based on the final recommendations 	[name], Distinguished Statistician

2. List of Abbreviations and Definitions of Terms

Abbreviation	Definition
AE	Adverse Event

Abbreviation	Definition
AVVQ	Aberdeen Varicose Vein Questionnaire
CEAP	Clinical, Etiological, Anatomical, and Pathophysiological Classification
CIP	Clinical Investigation Plan
CRF	Case Report Form
DUS	Duplex Ultrasound
DVT	Deep Vein Thrombosis
EGIT	Endovenous glue induced thrombosis
EHIT	Endovenous heat induced thrombosis
EQ-5D	EuroQoL 5 Dimensions Standardized Quality of Life Survey
EVLA	Endovenous Laser Ablation
ETA	Endovenous Thermal Ablation

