With these assumptions, a total of 22 subjects (evaluable; 11 in each arm) in the VenaSeal vs. ETA study and 10 subjects (evaluable; 5 in each arm) in VenaSeal vs. surgical stripping study will yield 90% power to reject the null hypothesis in favor of the alternative hypothesis of superiority in each study.

Closure rate

Closure rate is a generally used measure to determine the long-term success of venous reflux disease treatment. Literature may report on closure rate, occlusion rate, or recanalization rate at various moments in time. The endpoint used in this study focuses on the closure rate measured at 6 months.

To calculate the sample size based on historical data on closure rate, a literature search was conducted using the Pubmed database of clinical literature. Any literature older than 10 years was excluded from the analysis. Six-month closure rates for treatment of venous reflux disease with the VenaSeal™ closure device, any type of endovenous laser ablation and radiofrequency ablation, or surgical stripping were considered.

Closure rates were weighted within a treatment arm by multiplying the closure rate for that treatment with the sample size of the treatment arm. Table 2 below shows an overview of the literature that was used to calculate weighted closure rates that were used for sample size calculations.

Table 2: Closure Rates for Treatment of Venous Reflux Disease

Author	Year	Treatment	Follow-up	Sample size (# pts, ITT)	Closure/occlusion rate
Brittenden	2015	ETA: Laser	6M	212	83.0%
Bozoglan	2016	ETA: Laser	6M	60	100.0%
Eroglu	2018	ETA: Laser	6M	175	95.1%
Sydnor	2017	ETA: Laser	6M	100	100%
Wozniak	2016	ETA: Laser	6M	56	100%
Mese	XXXX	ETA: Laser	6M	60	100%
Atasoy	2015	ETA: Laser	6M	44	100%
Calik	2019	ETA: Laser	6M	200	95.6%
Lane	2016	ETA: RFA	6M	82	93.0%
Beteli	2017	ETA: RFA	6M	43	95.3%
Eroglu	2018	ETA: RFA	6M	175	94.1%
Sydnor	2017	ETA: RFA	6M	100	97.3%
Mendes	2016	ETA: RFA	6M	18	80.0%
Wozniak	2016	ETA: RFA	6M	54	100%
Mese	2015	ETA: RFA	6M	60	95.0%
Yang	2013	ETA: RFA	6M	100	99.0%
Morrison	2018	ETA: RFA	6M	114	96.2%
Creton	2010	ETA: RFA	6M	295	98.6%
Chan	2017	VenaSeal™	6M	57	90.3%
Almeida- FIH	2013	VenaSeal™	6M	38	92.1%
Gibson - WAVES	2016	Venaseal™	6M	70	98.0%
Proebstle- eSCOPE	2015	VenaSeal™	6M	70	91.4%
Morrison- VeClose	2018	VenaSeal™	6M	108	99.0%
Brittenden	2015	Surgical stripping	6M	294	84.4%
Jia	2010	Surgical stripping	6M	26	89.5%

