7.9.1.2 Analysis of Key Secondary Endpoints

7.9.1.2.1 Hypothesis

For key secondary endpoint of return to work, the following hypothesis will be tested:

$$H_0: S_A(t) = S_C(t)$$

$$H_a: S_A(t) \neq S_C(t)$$

Where $S_A(t)$ and $S_C(t)$ are the survival functions for freedom from return to work for the VenaSeal™ system arm and ETA or surgical stripping arm, respectively.

For the other key secondary endpoint of primary target vein closure rate at 6 months, the following hypothesis will be tested:

$$H_0: S_A(t) \leq S_C(t) - 10\%$$

$$H_a: S_A(t) > S_C(t) - 10\%$$

Where $t = 6$ months, and $S_A(t)$ and $S_C(t)$ are the survival functions for freedom from vessel re-opening at 6 months in the VenaSeal™ system arm and the ETA or surgical stripping arm, respectively and -10% is the non-inferiority margin.

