7.9.1.2.2 Endpoint Definition

Return to work is defined as the time in days patients need following a procedure to return to work. Employment status will be captured for all patients. Only patients who have an active employment status (employed or independent worker, including stay at home parents) will be included in the analysis for return-to-work time. Information will be captured on the category of occupation to be able to distinguish between physical and sedentary work. Patients will be censored at the time of study exit.

The other key secondary endpoint to be assessed is the primary target vein closure rate after index treatment. The primary target vein should be the saphenous vein (GSV, SSV, accessory saphenous veins) which at the investigator's discretion is most likely responsible for the greatest portion of the patient's symptoms or pathology. This vein will be treated first.

For subjects treated with the VenaSeal™ system or ETA, anatomic closure of the primary target vein is defined as Doppler ultrasound (DUS) showing primary target vein closure along the entire treated vein segment with no discrete segments of patency exceeding 5 cm. Any areas with >5 cm patency will be measured, and information will be collected on the location of the patency, length of the patency (cm), diameter of the patency (mm), the presence of flow (Y/N), the presence of reflux (Y/N), and the presence of thrombus (Y/N). For subjects treated with surgical stripping, anatomic closure of the primary target vein is defined as the absence of clinically significant refluxing truncal vein incompetency and no discrete segments of patency exceeding 5 cm in the primary target vein. Any areas with vein remnants will be measured and information will be collected on the location of the remnant, length of the remnant (cm), the presence of flow (Y/N), the presence of reflux (Y/N), and the presence of thrombus (Y/N). Lack of anatomic closure on the date of the index procedure will not be considered relevant to this endpoint, since some treatments may not achieve closure immediately.

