7.9.1.2.4 Analysis Methods

For the return to work endpoint, a Kaplan-Meier survival estimator will be used to estimate the survival functions for both the VenaSeal™ and the control arm (i.e., ETA or Surgical Stripping). Day zero is the date of the index procedure. The censoring time is the time to study exit, the later of either the last contact date or the discontinuation date, or the time point for analysis, whichever comes first. A cumulative incidence figure will be produced to compare the two treatments. A log-rank test will be used to test whether the survival distributions differ between the treatment groups. If a patient is reported to have returned to work, but the date of return is unknown, the return date will be imputed from the date of the follow-up visit. For those who have returned to work, the median, Q1, Q3, minimum, and maximum will summarize the number of days to return to work, as well as the number who have not returned to work in each treatment arm.

The treatment effect for primary target vein closure at 6 months, one of the key secondary endpoints, is the difference in the survival curves at time t for each randomized study. A Kaplan-Meier survival estimator will be used to estimate each curve. Day zero is the date of the index procedure. The censoring time is the time to last study visit (scheduled or unscheduled), the time point for analysis, or time to exit, whichever comes first. The non-inferiority test for treatment (VenaSeal) versus control (ETA or Surgical Stripping) will be performed using the test statistic proposed in da Silva, Logan and Klein (2009)³. The Z test statistic will calculate $S_A(t) - S_C(t) + 0.10$ for the numerator where t is at 6 months and the square root of the sum of the Greenwood's variance estimators for each of $S_A(t)$ and $S_C(t)$ in the denominator.

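### Six-month closure is defined and sized as vein status at 6 months but tested as freedom from re-opening up to 6 months, so the stated 80% power does not describe the test

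*SAP*

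**What the plan says.** Protocol 5.2.2 gives the endpoint as "Anatomic closure of the primary target superficial truncal vein at 6 months, defined as DUS showing vein closure along the entire treated vein segment"; an open segment longer than 5 cm counts against closure. For stripping it is absence of a refluxing or residual vein. Protocol 14.1.2 and SAP 6.1.2 size it on that basis. The SAP's wording is "The endpoint used in this study focuses on the closure rate measured at 6 months". The inputs are literature 6-month closure rates of 95% (VenaSeal), 95.4% (ETA) and 84.8% (stripping), a 10-point margin, and a Farrington-Manning test at one-sided 0.0167.

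The analysis sections of the SAP describe something else. The hypothesis in 7.9.1.2.1 concerns "survival functions for freedom from vessel re-opening at 6 months". In 7.9.1.2.4, "A Kaplan-Meier survival estimator will be used to estimate each curve", and the denominator of the test statistic is "the square root of the sum of the Greenwood's variance estimators". Observation is censored at the last study visit, the analysis time point or exit, whichever is earliest. The version 3.0 entry in the SAP history explains the change: "anatomic closure endpoints all revised use a time-to-first-event analysis to allow for censoring and incorporation of unscheduled follow-up visits". One allowance is made, in 7.9.1.2.2: "Lack of anatomic closure on the date of the index procedure will not be considered relevant to this endpoint".

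DUS is scheduled at Day 7 and Day 30 before the 6-month visit (protocol 10.5). The windows are days 5 to 9, 23 to 37 and 154 to 210 (protocol 10.2, Table 8).

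**The concern.** Status at a visit and absence of an event up to that visit are different estimands. They can classify the same vein differently, and they treat a missing 6-month scan differently. This is one of two key secondary endpoints under multiplicity control, it carries a non-inferiority claim, and its row (264) is the largest in the sample size table for the ETA study (protocol Table 19, SAP Table 4). If the sizing describes one endpoint and the test another, the power statement has no test attached to it, and the confirmatory conclusion answers a question that protocol 5.2.2 does not ask.

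**Working it through.** **How each document classifies the same subject**

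| Course of the primary target vein | Protocol 5.2.2 | SAP 7.9.1.2 |
|---|---|---|
| Closed at index, open at Day 7 or 30, closed at 6 months | Success | Failure: the first re-opening is the event and a later closed scan cannot undo it |
| Not closed at index, open at Day 7, closed at 6 months | Success | Not settled: only the index-date scan is excused, yet a vein that was never closed has not clearly re-opened |
| No 6-month DUS | No outcome (protocol 14.7: no imputation) | Censored at the last visit |
| First found open on, say, day 200 | Failure at the 6-month visit | Depends on t, which is given as 6 months and not in days; if t is day 182, there is no event by t |

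**Reproducing the stated size (ETA study).** Inputs from SAP 6.1.2: pA = 0.95, pC = 0.954, margin 0.10, n = 119 per arm, one-sided 0.0167 (z = 2.127).

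- Signal: 0.95 − 0.954 + 0.10 = 0.096.
- Rates restricted to the null (difference of exactly −0.10): 0.8726 and 0.9726. Null SE = √[(0.8726×0.1274 + 0.9726×0.0274)/119] = 0.0340.
- SE under the alternative = √[(0.95×0.05 + 0.954×0.046)/119] = 0.0277.
- Power = Φ[(0.096 − 2.127×0.0340)/0.0277] = Φ(0.851) = 80.3%.

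The stated 119 per arm is confirmed. For stripping at 44 per arm the same method gives 78.2%, close to the stated 80%.

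**The test the SAP specifies.** Without censoring, Greenwood's variance is S(1−S)/n, so the SAP statistic becomes an unpooled Z:

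Power = Φ[(SA − SC + 0.10)/SE − 2.127], SE = √{[SA(1−SA) + SC(1−SC)]/119}.

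With S equal to the sizing rates: 0.096/0.0277 − 2.127 = 1.337, so power is 90.9%. The change of variance alone raises the figure by about 11 points.

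Next, let some veins open early and close by 6 months, which lowers S but leaves 6-month status unchanged. The documents give no rate for this, so 1, 2 and 3 points are assumptions.

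| Transient openings | 1 point | 2 points | 3 points |
|---|---|---|---|
| Both arms | 85.1% | 79.2% | 73.7% |
| VenaSeal only | 79.8% | 65.0% | 48.9% |
| ETA only | 93.6% | 95.6% | 97.0% |

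Example, VenaSeal only, 2 points: SA = 0.93, signal 0.076, SE 0.0303, Φ(0.384) = 65.0%.

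The stripping study at 44 per arm behaves similarly: 85.6% with none, 79.2% with 2 points in both arms.

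**The case against.** The strongest defence has four parts. First, the change is disclosed with a reason in the SAP version history, and protocol 14 and SAP 7.12 allow method changes to be explained in the study report unless a principal feature changes. Second, Kaplan-Meier freedom from recanalization with a 10-point margin has a precedent in the five-year extension of this product's pivotal trial (protocol 4.1). It also has an advantage: a vein that re-opens, is retreated and is closed at 6 months counts as a failure, whereas 6-month status would count it as a success unless a rule is added. Third, the early data in protocol 4.1 suggest that transient opening is rare with VenaSeal: the single-arm post-market study found all 70 veins closed at 7 days and 1 month. Fourth, under the SAP's own test, power stays near or above 80% until transient openings reach about 2 points in both arms or 1 point in VenaSeal alone.

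Much of this stands. Kaplan-Meier is a legitimate choice and its power may well be adequate. But 70 of 70 is compatible with a rate of up to about 4% (1 − 0.05^(1/70) = 4.2%, treating veins as independent), so it does not exclude the scenarios above. Disclosure does not remove the conflict either: SAP 6.1.2 still states the proportion hypothesis, the Farrington-Manning test and the 80% alongside the new analysis, and protocol version 5.0 still has the status endpoint. What a multiplicity-controlled endpoint measures is arguably a principal feature.

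A reader might infer three stronger things that the documents do not support:

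- **Any open scan after the index day is a final failure.** The SAP never defines the event in those terms. That reading combines the time-to-first-event label with the index-date allowance, while the hypothesis speaks of re-opening.
- **The study is underpowered for closure.** The direction is unknown; the calculation gives values on both sides of 80%.
- **Subjects without a 6-month scan are scored as closed.** They are censored and leave the risk set at their last visit.

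**Conclusion.** The mismatch holds in the current texts. The protocol and the sizing use DUS status at 6 months; the SAP tests freedom from re-opening, with a different variance. At least one plausible course (closed, open early, closed at 6 months) changes from success to failure, and another (not closed at index, closed later) cannot be classified from the text. The stated 80% was derived for a test that will not be run. For the SAP test, the figure at 119 per arm is about 91% with no transient openings, and 49% to 97% across the assumed scenarios of 1 to 3 points. These values rest on the sizing closure rates, on no censoring and on transient-opening rates that the documents do not supply, so they show sensitivity and are not a forecast. The point should be corrected before the closure analysis is run.

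**What to change.** Use one estimand in both documents, by either route:

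1. **Status at 6 months.** Make DUS status at the 6-month visit the confirmatory test, with Farrington-Manning as sized. State how a vein retreated before 6 months counts. Keep the Kaplan-Meier analysis as supportive.
2. **Sustained closure.** Keep Kaplan-Meier and amend protocol 5.2.2 to sustained closure through 6 months. Define the event, including veins not closed at index and open scans at Day 7 or 30, and give t in days with a rule for 6-month visits that fall after it. Replace the test and power in SAP 6.1.2 with those of the analysis to be run, and report 6-month DUS status as a sensitivity analysis.

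Under either route, tabulate by arm the veins that were open at Day 7 or 30 and closed at 6 months.

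The cost is protocol and SAP wording, one extra table from scans already scheduled, and, under the second route, a restated power figure that may go up or down. No new data are needed.

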7.9.1.2.2 Endpoint Definition

Return to work is defined as the time in days patients need following a procedure to return to work. Employment status will be captured for all patients. Only patients who have an active employment status (employed or independent worker, including stay at home parents) will be included in the analysis for return-to-work time. Information will be captured on the category of occupation to be able to distinguish between physical and sedentary work. Patients will be censored at the time of study exit.

The other key secondary endpoint to be assessed is the primary target vein closure rate after index treatment. The primary target vein should be the saphenous vein (GSV, SSV, accessory saphenous veins) which at the investigator's discretion is most likely responsible for the greatest portion of the patient's symptoms or pathology. This vein will be treated first.

For subjects treated with the VenaSeal™ system or ETA, anatomic closure of the primary target vein is defined as Doppler ultrasound (DUS) showing primary target vein closure along the entire treated vein segment with no discrete segments of patency exceeding 5 cm. Any areas with >5 cm patency will be measured, and information will be collected on the location of the patency, length of the patency (cm), diameter of the patency (mm), the presence of flow (Y/N), the presence of reflux (Y/N), and the presence of thrombus (Y/N). For subjects treated with surgical stripping, anatomic closure of the primary target vein is defined as the absence of clinically significant refluxing truncal vein incompetency and no discrete segments of patency exceeding 5 cm in the primary target vein. Any areas with vein remnants will be measured and information will be collected on the location of the remnant, length of the remnant (cm), the presence of flow (Y/N), the presence of reflux (Y/N), and the presence of thrombus (Y/N). Lack of anatomic closure on the date of the index procedure will not be considered relevant to this endpoint, since some treatments may not achieve closure immediately.

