COMPARATOR	TOTAL NUMBER OF CONSIDERED STUDIES	TOTAL SAMPLE SIZE IN CONSIDERED STUDIES	WEIGHTED AVERAGE CLOSURE RATE AT 6M
VENASEAL™	5	343	95.0%
ETA	14	1948	95.4%
SURGICAL STRIPPING	2	320	84.8%

The null hypothesis on this key secondary endpoint is that the closure rate at 6 months in the VenaSeal™ system arm will have less than or equal to that in the control (ETA or surgical stripping) arm minus a clinically relevant difference of 10%. The alternative hypothesis is that the closure rate at 6 months in the VenaSeal™ system arm will be greater than that in the control arm minus a clinically relevant difference of 10%. Rejection of the null hypothesis will signify that the treatment with the VenaSeal™ system is not inferior to the treatment with ETA or surgical stripping.

Specifically, the null (H_0) and alternative (H_a) hypotheses are:

$H_0: \pi_A \leq \pi_C - 10\%$
$H_a: \pi_A > \pi_C - 10\%$

Where π_A and π_C are the closure rate at 6 months in the VenaSeal™ system arm and the ETA or surgical stripping arm.

The parameter assumptions are:

- $\pi_A = 95\%$ in the VenaSeal™ system arm and $\pi_C = 95.4\%$ and 84.8% in ETA and surgical stripping arm, respectively
- Likelihood Score (Farrington & Manning) test with one sided $\alpha = 0.0167$
- 1:1 randomization
- 10% attrition rate.

With these assumptions, a total of 264 subjects (238 evaluable, 119 in each arm) will yield 80% power to reject the null hypothesis in favor of the alternative hypothesis of non-inferiority to the ETA arm. A total of 98 subjects (88 evaluable, 44 in each arm) will yield 80% power to reject the null hypothesis in favor of the alternative hypothesis of non-inferiority to the surgical stripping arm.

Overall Sample Size Evaluation

Power Analysis and Sample Size (PASS) was used to compute sample size. Based on the above fixed sample size calculations, the total sample size in the VenaSeal vs ETA study will be 264 to demonstrate the success on each primary endpoint with at least 90% power **Table 19**.

The total sample size in the VenaSeal vs Surgical Stripping Study will be 108 subjects due to the enrollment closure on 22-Feb-2022.

Table 19: Sample Size for Randomized Studies

Primary or Key Secondary Endpoint	Total Sample Size: VenaSeal and ETA Arms	Total Sample Size: VenaSeal and Surgical Stripping Arms
VenousTSQe at 30 days	237	237
VenousTSQs at 30 days	237	237
Elimination of truncal reflux at index procedure	227	220
Return to work	22	10

Closure rate at 6 months	264	98

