4.2 Secondary Objectives

4.2.1 Key Secondary Endpoints in the Randomized Studies

The key secondary objectives are to compare the VenaSeal™ system to surgical stripping and ETA in achieving the anatomical closure of superficial truncal veins at 6 months, and the ability to return to work post-index procedure.

Return to Work

Return to work is defined as the time in days patients need following a procedure to return to work.

Anatomical Closure

Anatomical closure is defined as DUS showing vein closure along the entire treated vein segment with no discrete segments of patency exceeding 5 cm for subjects in the arms treated with the VenaSeal™ system or ETA. In the surgical stripping arm, it is defined as clinically significant refluxing truncal vein incompetency and no discrete segments of patency exceeding 5 cm.

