Table 3 shows an overview of the weighted average closure rates at 6 months that were used to calculate the sample size for this endpoint.

Table 3: Weighted Average Closure Rate

Comparator	Total number of considered studies	Total sample size in considered studies	Weighted average closure rate at 6M
VenaSeal™	5	343	95.0%
ETA	18	1948	95.4%
Surgical stripping	2	320	84.8%

The null hypothesis on this key secondary endpoint is that the closure rate at 6 months in the VenaSeal™ system arm will have less than or equal to that in the control (ETA or surgical stripping) arm minus a clinically relevant difference of 10%. The alternative hypothesis is that the closure rate at 6 months in the VenaSeal™ system arm will be greater than that in the control arm minus a clinically relevant difference of 10%. Rejection of the null hypothesis will signify that the treatment with the VenaSeal™ system is not inferior to the treatment with ETA or surgical stripping.

Specifically, the null (H_0) and alternative (H_a) hypotheses are:

$$H_0: \pi_A \leq \pi_C - 10\%$$

$$H_a: \pi_A > \pi_C - 10\%$$

Where π_A and π_C are the closure rate at 6 months in the VenaSeal™ system arm and the ETA or surgical stripping arm.

The parameter assumptions are:

- $\pi_A = 95\%$ in the VenaSeal™ system arm and $\pi_C = 95.4\%$ and 84.8% in ETA and surgical stripping arm, respectively
- Likelihood Score (Farrington & Manning) test with one sided $\alpha = 0.0167$
- 1:1 randomization
- 10% attrition rate

With these assumptions, a total of 264 subjects (238 evaluable, 119 in each arm) will yield 80% power to reject the null hypothesis in favor of the alternative hypothesis of non-inferiority to the ETA arm. A total of 98 subjects (88 evaluable, 44 in each arm) will yield 80% power to reject the null hypothesis in favor of the alternative hypothesis of non-inferiority to the surgical stripping arm.

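### The stripping-arm success criterion for the formally tested 6-month closure endpoint differs between the protocol and the SAP, and SAP 4.2.1 drops the words that make it a success criterion

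*SAP*

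**What the plan says.** The protocol, section 5.2.2, defines success after stripping as "or the absence of refluxing or residual primary target vein after surgical stripping procedures". It sets no length threshold and does not grade the reflux. The same rule appears in the synopsis and in sections 5.2.3, 10.5 and 10.13.

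The SAP, section 7.9.1.2.2, defines success after stripping as "the absence of clinically significant refluxing truncal vein incompetency and no discrete segments of patency exceeding 5 cm", applied to the primary target vein. Section 7.9.1.4 uses essentially this rule for the other closure endpoints and for technical success.

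The SAP, section 4.2.1, describes the stripping-arm criterion thus: "it is defined as clinically significant refluxing truncal vein incompetency and no discrete segments of patency exceeding 5 cm". The words *absence of* are missing.

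The comparison is a non-inferiority test: the null hypothesis puts the VenaSeal rate at or below the control rate "minus a clinically relevant difference of 10" percentage points. Sections 6.1 and 7.5 of the SAP keep this endpoint in the formal testing scheme of the stripping study. Section 7.9.1.2.3 adds a superiority test if non-inferiority is met.

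On sample size, both documents say: "A total of 98 subjects (88 evaluable, 44 in each arm) will yield 80% power". Protocol section 14.1.2 assumes 95% closure for VenaSeal and "84.8% in ETA and surgical stripping arm, respectively" for the controls. The SAP presents the source table as an "overview of the weighted average closure rates at 6 months that were used to calculate the sample size for this endpoint".

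**The concern.** The two rules are not paraphrases of each other, so the same patient can be a failure in one document and a success in the other. That matters in an endpoint with a formal non-inferiority claim, a follow-on superiority claim, and a p-value that also affects the threshold for return to work under section 7.5.

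The qualifier is a second problem. Neither document says what makes reflux clinically significant or who decides. The trial is unblinded (protocol section 6), ultrasound is done by site technicians or investigators (protocol section 10.5), and the only core laboratory described is for ulcers (protocol section 13.3). The qualifier also applies to the stripping arm alone.

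If the criterion is settled only after the data have been seen, the choice could affect the result.

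**Working it through.** **1. The rules side by side, for a stripped leg at 6 months**

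| Finding on ultrasound | Protocol 5.2.2 | SAP 7.9.1.2.2 |
|---|---|---|
| No residual vein, no reflux | success | success |
| Patent remnant of 5 cm or less, no clinically significant reflux | failure | success |
| Patent remnant over 5 cm | failure | failure |
| Clinically significant reflux | failure | failure |

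Every leg that passes the protocol rule passes the SAP rule, but not the reverse. In the same legs, the SAP success rate is therefore equal to or higher than the protocol success rate. By how much is unknown: the documents give no count of legs in the second row.

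**2. What one leg is worth**

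The study closed with 108 subjects. With the planned 10% attrition, 108 × 0.90 / 2 = 48.6, so about 48 per arm. One reclassified stripping leg moves the control rate, and hence the difference, by 1/48 = 2.1 points. Five such legs move it by 5/48 = 10.4 points, about the whole margin. This ignores censoring in the Kaplan-Meier estimate and needs no assumed control rate.

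**3. The plan's own sample size reproduces**

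Inputs, from SAP 6.1.2 and protocol 14.1.2: VenaSeal 95%, stripping 84.8%, margin 10 points, 1:1 allocation, "Likelihood Score (Farrington & Manning) test with one sided" alpha of 0.0167, 10% attrition.

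- Stripping rate: (294 × 84.4% + 26 × 89.5%) / 320 = 84.8%.
- Power, by summing over both binomial distributions with the score statistic: 79.9% at 43 per arm and 83.7% at 44 per arm. So 44 is the first size that reaches 80%. (The asymptotic formula gives 78.2% at 44.)
- Attrition: 88 / 0.90 = 97.8, rounded up to 98.

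**4. Sensitivity to the stripping rate (illustration only)**

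Rates other than 84.8% are assumptions. VenaSeal is held at 95%.

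| Stripping rate | Score test, 0.0167, 44 per arm | Score test, 0.0167, 48 per arm |
|---|---|---|
| 84.8% | 84% | 86% |
| 86% | 80% | 83% |
| 90% | 62% | 67% |
| 95% | 33% | 37% |

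The SAP will not run that test at that level. Section 7.5 tests the key secondaries of the stripping study at 0.05, 0.025 or 0.0125, depending on earlier results. Section 7.9.1.2.4 uses a Kaplan-Meier difference with Greenwood variances, which without censoring is an unpooled Z statistic. Its exact power at 48 per arm is:

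| Stripping rate | one-sided 0.05 | 0.025 | 0.0125 |
|---|---|---|---|
| 90% | 89% | 84% | 76% |
| 95% | 75% | 67% | 54% |

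Power falls as the control rate rises in either table, but less steeply under the planned analysis.

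**The case against.** The strongest reply is that this is a wording matter in a sub-study already closed to enrolment. Remnant length and reflux are recorded, so either version can be computed, and the SAP rule is the fairer one. It gives stripping the same 5 cm tolerance as VenaSeal and makes non-inferiority harder, not easier, to show. All of that is fair, and it bears on which rule to choose. It does not make the endpoint defined: two approved documents still give two answers for the same leg.

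Four stronger readings are tempting, and the documents do not support them.

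- *The 80% power fits only one of the two definitions.* The 84.8% is a weighted average of two published reports, and neither document says how those reports defined success. The rate may match either rule or neither, and would suit both if few legs fall between them. The most that can be said is that one rate cannot serve both rules if they give materially different results.
- *SAP 4.2.1 is a third, opposite definition.* It is almost certainly a drafting slip. It pairs the phrase with the 5 cm condition, which makes sense only as success, and the operative sections (7.9.1.2.2 and 7.9.1.4) include the missing words.
- *The SAP changed the definition without logging it.* The SAP history records changes between SAP versions. Earlier SAP text is not available, so the wording may have been there from the start.
- *The protocol rule should govern the confirmatory test.* That is a preference. The protocol rule tolerates up to 5 cm of patency after VenaSeal but no residual vein after stripping.

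**Conclusion.** The point holds as a conflict of definition. A formally tested endpoint has two working success criteria for the stripping arm, plus one section that needs a correction. They disagree on legs with a short patent remnant and no clinically significant reflux. Each such leg is worth about 2 points against a 10-point margin, on the assumption of about 48 evaluable subjects per arm and no censoring. How many such legs there are cannot be known from the documents.

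The direction is known: the SAP rule keeps or raises the control rate. That makes non-inferiority, and any later superiority claim, harder to show.

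The sample-size arithmetic stands. The falls in power shown above rest on assumed stripping rates and are not an estimate of what the SAP rule would do.

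**What to change.** Before database lock:

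1. State one stripping-arm criterion for the confirmatory test, in identical words, in protocol 5.2.2 and SAP 4.2.1, 7.9.1.2.2 and 7.9.1.4, with a sentence giving the reason for the choice.
2. Restore *absence of* in SAP 4.2.1.
3. Define *clinically significant* from the reflux and remnant-length data already recorded, or delete it.
4. Report the version not chosen as a named sensitivity analysis.
5. Add to the sample-size section that 84.8% is a literature rate not linked to either criterion, and show power over a range of stripping rates, labelled as illustration.

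The cost is a SAP correction if the protocol rule is kept, or a short protocol amendment with a SAP correction if the 5 cm rule is kept. No new data are needed, since SAP 7.9.1.2.2 already collects remnant length and the presence of reflux.
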